# CONFIDENTIAL

SAP	statistical analysis plan
screen	The act of determining if an individual meets minimum requirements to become part of a pool of potential candidates for participation in a clinical study.
SoA	Schedule of Activities
study drug	See "study intervention"
study intervention	Any investigational intervention, marketed product, placebo, or medical device intended to be administered to a study participant according to the study protocol
ТВ	tuberculosis
TBL	total bilirubin level
TEAE	Treatment-emergent adverse event: An untoward medical occurrence that emerges during a defined treatment period, having been absent pretreatment, or worsens relative to the pretreatment state, and does not necessarily have to have a causal relationship with this treatment.
TST	tuberculin skin test
UAS7	Urticaria Activity Score Over 7 Days
ULN	upper limit of normal
UPDD	Urticaria Patient Daily Diary
USA	United States of America; also United States
WBC	white blood cell
WOCBP	women of childbearing potential (see Appendix 10.4)

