5.3.2. Definition of Baseline and Postbaseline Measures

The baseline value for Period 2 is defined as the last nonmissing measurement on or before the date of first study drug administration (expected at Week 0). The baseline value for Period 3 is the last available value before the initial dose in Period 3 (expected at Week 12). Other definitions of the baseline value may be used to conduct additional supporting analyses.

A number of efficacy outcome measures are in the form of weekly scores derived from patient daily diary data. For these measures, the weekly score will be derived from the 7 days immediately prior to the study visit. The baseline score will be derived from the 7 days prior to Day 1 (Visit 2) for Period 2, and 7 days prior to Day 85 (Visit 9) for Period 3.

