5.7. Safety Analyses

The general methods used to summarize safety data, including the definition of baseline value are described in Section 5.3.2.

Safety analyses will include data after rescue, unless otherwise stated, and patients will be analyzed according to the investigational product to which they were randomized at Week 0 (Visit 2). Additional analyses may be conducted using data after rescue to systemic therapy for some safety topics such as systemic treatment-emergent adverse events (TEAEs), and serious adverse events (SAEs). Safety analyses will take place using the safety population defined in Section 5.3.1.

Safety topics that will be addressed include the following: AEs, clinical laboratory evaluations, vital signs and physical characteristics, Columbia Suicide Severity Rating Scale (C-SSRS), the Self-Harm Supplement Form, safety in special groups and circumstances, including adverse events of special interest (AESI) (see Section 5.7.5), and investigational product interruptions.

Unless otherwise specified, by-visit summaries will include planned on-treatment visits. For tables that summarize events (such as AEs, categorical lab abnormalities, shift to maximum value), post-last dose follow-up data will be included. Follow-up data is defined as all data occurring up to 30 days (planned maximum follow-up time) after last dose of treatment including rescue, regardless of study period except for deaths and malignancies. For deaths and malignancies, all available follow-up data up to the end of the study will be included. Listings will include all safety data.

For selected safety assessments, descriptive statistics may be presented for the last measure observed during post-treatment follow-up (up to 30 days after the last dose of treatment including rescue, regardless of study period).

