5.7.2. Adverse Events

Adverse events are recorded in the eCRFs. Each AE will be coded to system organ class (SOC) and preferred term (PT) using the Medical Dictionary for Regulatory Activities (MedDRA) version that is current at the time of database lock. Severity of AEs is recorded as mild, moderate, or severe.

A TEAE is defined as an event that either first occurred or worsened in severity after the first dose of study treatment and on or prior to the last visit date during the analysis period. For each event classification term, the number of participants experiencing a TEAE with that classification term will be tabulated. For this study, the TEAEs should be counted by periods: TEAEs for Period 2 for V2-V9; TEAEs for Period 3 for V10-V16; TEAEs for Period 4 after V16.

Treatment-related TEAEs are defined as events that are indicated by the investigator on the eCRF to be related to treatment. For events that are gender specific, the denominator and computation of the percentage will include only participants from the given gender.

Adverse events are classified based upon the MedDRA PT. The MedDRA Lowest Level Term (LLT) will be used in defining which events are treatment-emergent. The maximum severity for each LLT during the baseline period up to first dose of the study medication will be used as baseline. If an event with missing severity is preexisting during the baseline period, and persists during the treatment period, then the baseline severity will be considered mild for determining TEAE (that is, the event is treatment-emergent if the severity is coded moderate or severe postbaseline and not treatment-emergent if the severity is coded mild postbaseline). If an event occurring postbaseline has a missing severity rating, then the event is considered treatment-emergent. The day and time for events where onset is on the day of the first dose of study treatment will both be used to distinguish between pretreatment and posttreatment in order to derive treatment-emergence. Should there be insufficient data for AE start date to make this comparison (for example, the AE start year is the same as the treatment start year, but the AE start month and day are missing), the AE will be considered treatment-emergent.

In an overview table, the number and percentage of subjects who experienced a TEAE or serious adverse event (SAE), died due to an AE, or discontinued from study due to an AE will be summarized by treatment.

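### SAP 5.7.2 counts TEAEs by period but states only a pre-Week 0 severity baseline, so an event that emerged in Period 2 can qualify again in Period 3

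*SAP*

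**What the plan says.** SAP 5.7.2 sets the test that a TEAE must meet: "first occurred or worsened in severity after the first dose of study treatment and on or prior to the last visit date during the analysis". One more word ends that clause, so the upper limit is set by the analysis period in question. For severity it states: "The maximum severity for each LLT during the baseline period up to first dose of the study medication will be used as baseline". It then asks for a separate count in each period, using these windows: "TEAEs for Period 2 for V2-V9; TEAEs for Period 3 for V10-V16; TEAEs for Period 4 after V16". It gives no AE severity baseline for Period 3 or Period 4. Nor does it say whether an event is placed in a period by its onset, by its worsening or by being present.

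SAP 5.7 opens the safety section with a cross-reference: "The general methods used to summarize safety data, including the definition of baseline value are described in Section 5.3.2". SAP 5.3.2 says: "The baseline value for Period 3 is the last available value before the initial dose in Period 3". It has no Period 4 baseline.

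On attribution, the Safety population in SAP 5.3.1 follows the treatment actually received in each period. SAP 5.7 instead analyses patients by the product randomized at Week 0.

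Protocol 9.4.5 defines a TEAE relative to baseline without saying which one. The glossary in Protocol Appendix 7 (10.7) describes it as "An untoward medical occurrence that emerges during a defined treatment period, having been absent pretreatment, or worsens relative to the pretreatment state".

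**The concern.** In a crossover, a per-period TEAE table should show what emerged on the treatment given in that period. This needs a reference state taken just before that treatment began. SAP 5.7.2 moves the upper limit of the window with the analysis period, but leaves both the start date and the severity reference at Week 0. A term that emerged on the first treatment therefore stays above baseline for the rest of the study.

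The situation is likely to arise. The schedule of activities has infusions at V8 (Week 10) and at V9 (Week 12, the first Period 3 dose), with no washout. Protocol 4.2 gives a half-life of about 2 weeks. Some Period 2 events can be expected to be present at the crossover or to recur soon after. The by-treatment frequency tables and the Fisher's exact tests in SAP 5.7.2 would use the resulting counts.

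**Working it through.** The plan states no figure to reproduce, so this is a check of definitions followed by an illustration of size.

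**1. The rule as written.** Score severity 0 (none), 1 (mild), 2 (moderate), 3 (severe). For one LLT, let b be the maximum before Week 0, s2 the maximum in Period 2 and s3 the severity recorded in Period 3 (at least 1).
- Period 2 TEAE: s2 > b.
- Period 3 TEAE under the baseline in SAP 5.7.2: s3 > b.
- Period 3 TEAE if the baseline is the maximum up to the first Period 3 dose: s3 > max(b, s2).

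**2. Patterns that qualify in both periods under SAP 5.7.2** (s2 > b and s3 > b):
- b = 0: 3 × 3 = 9
- b = 1: 2 × 2 = 4
- b = 2: 1 × 1 = 1
- Total: 14

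**3. The same patterns with a Period 3 baseline.** Those with s3 no higher than s2 drop out: 6 + 3 + 1 = 10. Those with s3 above s2 remain: 3 + 1 + 0 = 4, and these are true worsening. These are counts of possible patterns, not expected frequencies.

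| Before Week 0 | Period 2 | Period 3 | Period 3 TEAE, SAP 5.7.2 baseline | Period 3 TEAE, Period 3 baseline |
|---|---|---|---|---|
| none | moderate | mild | yes | no |
| none | moderate | moderate | yes | no |
| mild | moderate | moderate | yes | no |
| none | mild | moderate | yes | yes |

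**4. Treatment column.** Under SAP 5.3.1, a recounted event in a participant who crossed from LY3454738 to placebo goes in the placebo column for Period 3. Under the sentence in SAP 5.7, it stays with LY3454738. The two rules give different tables.

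**5. Illustration of size.** From the documents: 60 randomized 3:1, so 45 and 15. Assumption, not in the documents: 10% to 30% of participants in each sequence carry a recounted event into Period 3, and none of them already counts in the receiving column. Attribution is by treatment received.
- Period 3 placebo column gains 45 × 0.10 to 0.30 = 4.5 to 13.5 of 45, or 10 to 30 percentage points.
- Period 3 LY3454738 column gains 15 × 0.10 to 0.30 = 1.5 to 4.5 of 15, or 10 to 30 points.
- At the same fraction in both sequences, the Period 3 difference moves by 0.
- If Periods 2 and 3 were pooled (60 per treatment), placebo would gain 4.5/60 to 13.5/60 = 7.5 to 22.5 points and LY3454738 1.5/60 to 4.5/60 = 2.5 to 7.5 points. The difference would move by at most 5 to 15 points.

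**The case against.** The strongest reply is that the definition requires an event to first occur or to worsen, and an event first occurs only once. One that starts in Period 2 and simply continues, unchanged or improving, does neither in Period 3. This stands: such an event need not be counted again. Recounting needs a new record, a recurrence, or placement by presence. SAP 5.7.2 excludes none of these, and a new record at lower severity is still above its only stated baseline.

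Second, SAP 5.7 sends the reader to 5.3.2, which has a Period 3 baseline. This also stands, so it is not settled that Period 3 events will be judged against Week 0. But 5.3.2 is a general rule for the last available value, while 5.7.2 gives a specific rule for AE severity. If 5.3.2 governs, the sentence in 5.7.2 is wrong for Period 3; if 5.7.2 governs, recounting can follow. The text needs correcting either way.

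Third, the Protocol glossary can be read as meaning before any study treatment, so it supports a per-period baseline without compelling one.

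A reader might infer that drug harms are systematically moved to placebo, with the contrast narrowed by 5 to 15 points. The documents do not support that. The figure needs pooling across periods, which the SAP does not specify, and attribution by treatment received, which SAP 5.7 contradicts.

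**Conclusion.** The point holds as a defect in a stated rule. One pre-first-dose severity baseline, combined with per-period counting, lets an LLT recorded in Period 3 at the same or lower severity than in Period 2 qualify in both periods. Whether this happens in practice depends on which SAP section governs and on how continuing events are recorded on the eCRF, which the documents do not give.

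Its reach is limited to the Period 3 and Period 4 TEAE tables and the related Fisher tests. The Period 2 comparison and the primary endpoint are unaffected, and the planned listings of all AEs allow manual review.

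Neither size nor direction can be fixed from the documents. With equal carry-over fractions, both Period 3 columns are inflated alike, and a net shift toward placebo appears only if periods are pooled by treatment received. Unequal fractions would move the Period 3 difference too, in a direction the documents do not indicate.

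It would also be wrong to infer that Period 4 events are credited to the crossover treatment. No study drug is given in Period 4; the gap there is that neither a severity baseline nor a treatment column is stated.

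**What to change.** In SAP 5.7.2, define the severity baseline by period:
- Period 2: maximum severity of each LLT before the first infusion at V2.
- Period 3: severity of each LLT ongoing at the first Period 3 infusion (V9).
- Period 4: severity ongoing at V16.

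Count an event in a period only if it starts, or worsens above that severity, after that point. The Period 3 window should then open at the V9 infusion; the current wording opens it at V10, one week later. Using severity ongoing at V9 means that an event that resolved in Period 2 and recurs in Period 3 counts as a new start. This differs from the maximum-to-date baseline used in the pattern count above, so the SAP should say explicitly which is meant.

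Reconcile treatment attribution between SAP 5.3.1 and 5.7, align the baseline wording with 5.3.2, and state how Period 4 events are displayed.

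The cost is SAP wording and one derived variable, with no new data. Some events will move out of the Period 3 and Period 4 counts.

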5.7.2.1. Serious Adverse Event Analyses

The number and percentage of patients who experienced an SAE (including the SAEs that led to death) during the study drug period will be summarized by treatment using MedDRA PT nested within SOC. Events will be ordered by decreasing frequency within SOC.

5.7.2.2. Other Significant Adverse Events

The number and percentage of patients who permanently discontinued from study treatment due to an AE (including AEs that led to death) during the study drug period will be summarized by treatment using MedDRA PT nested within SOC. Events will be ordered by decreasing frequency within SOC.

Fisher's exact test will be performed to compare percentages for each LY3454738 dose group and Placebo at both the SOC and PT levels.

5.7.3. Clinical Laboratory Evaluation

Laboratory analyses will include planned analytes only. Planned analytes are those specified in the protocol. Summaries will be provided in both Système International (SI) and United States (US) conventional (CN) units (when different). Limits from the performing lab will be used to define low and high. Analyses of laboratory values will be produced using the measurements collected at scheduled time points. All unscheduled assessments will appear only in data listings.

- **Box plots for observed values:** Values at each visit (starting at randomization) will be displayed in box plots for patients who have both a baseline and a result for the specified visit. Unplanned measurements will be excluded. Original-scale data will be used for the display. These box plots will be used to evaluate trends over time and to assess a potential impact of outliers on central tendency summaries. The box plot will be a notched box for each treatment with outliers displayed, individual measurements outside of reference limits will also be displayed using distinct symbols overlaying the box plot, and descriptive summary statistics will be included in a table below the box plot.
- **Box plots for change values:** Change from baseline to each visit will be displayed in box plots for patients who have both a baseline and a result for the specified visit. Change from baseline to last observation will also be summarized and analyzed for patients who have both baseline and at least 1 postbaseline result. Baseline will be the last non-missing observation in the baseline period. The last non-missing observation in the Dosing Period will be used as the last observation. Unplanned measurements will be excluded. The box plot will be a notched box for each treatment with outliers displayed, change from baseline to last observation will be summarized within the box plot of changes (rightmost column), and descriptive summary statistics will be included in a table below the box plot, along with a p-value using the ANCOVA model containing terms for treatment and the continuous covariate of baseline measurement. Type III sums of squares will be used. The significance of within-treatment group LSMean changes from baseline are different from zero using a t-statistic. In addition to the LSMeans and tests, the SD, minimum, Q1, median, Q3, and maximum will be displayed.

Alanine aminotransferase (ALT), aspartate aminotransferase (AST), and total bilirubin will not be included in this analysis as different ranges will be used as described in Section 5.7.5.

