																		(Section 8.2.7)
Symptom-directed		х	Х	Х	х	х	х	Х	х	Х	Х	Х	Х	Х	Х	Х	Х	Includes assessment of
physical																		skin at every visit
examination																		(Section 8.2.2)

	Screening								Treat	ment P	eriods							
	Period 1				Period	d 2						Р	ETV	Comments				
Visit number	V1	V2	V3	V4	V5	V6	V7	V8	V9	V10	V11	V12	V13	V14	V15	V16		
Weeks from randomization	-5	-	1	2	4	6	8	10	12	13	14	16	18	20	22	24		
Study day	-35	1	8	15	29	43	57	71	85	92	99	113	127	141	155	169		
Visit tolerance interval (days)		—	±1	±3	±3	±3	±3	±3	±3	±3	±3	±3	±3	±3	±3	±3		
Fasting visit		х							х							х		
12-lead ECG	x								х							Х	х	Locally read, performed before blood sampling
Chest x-ray (posterior– anterior view)	X																	Interpreted and reported by radiologist or pulmonologist. Not performed at screening if performed within 6 months before screening and if qualifying radiographs or equivalent imaging study and/or formal report are available for investigator's review. Locally performed.
Patient Diary (Election	ronic)																	-
Dispense electronic diary	X																	Includes Urticaria Patient Daily Diary (UPDD). The diary is completed daily.
Check electronic diary compliance		х	Х	Х	х	Х	х	х	х	х	Х	Х	х	х	х	х		

	Screening								Treat	ment P	eriods							
	Period 1	Period 2 Period 3 ETV												Comments				
Visit number	V1	V2	V3	V4	V5	V6	V7	V8	V9	V10	V11	V12	V13	V14	V15	V16		
Weeks from randomization	-5	-	1	2	4	6	8	10	12	13	14	16	18	20	22	24		
Study day	-35	1	8	15	29	43	57	71	85	92	99	113	127	141	155	169		
Visit tolerance interval (days)		-	±1	±3	±3	±3	±3	±3	±3	±3	±3	±3	±3	±3	±3	±3		
Fasting visit		Х							Х							Х		
Return electronic diary																		Participant should return the diary at Treatment Period ETV if the participant does not enter Post-Treatment Follow-Up period (Period 4).
Patient-Reported Outcomes (Paper)																		
DLQI		Х			Х		Х		Х			Х		Х		Х	Х	
Laboratory Tests an	d Sample Col	lectio	ns															
Hematology	Х	х	Х	Х	х	х	х	х	х	Х	Х	Х	Х	Х	Х	Х	Х	
Clinical chemistry	Х	х	х	х	х	х	х	х	х	Х	Х	х	х	Х	Х	х	Х	
Lipid panel		X							Х							x	x	For the fasting lipid profile, participants should not eat or drink anything except water for 12 hours prior to the test. Fasting is not required for the lipid panel at an ETV.
Urinalysis	Х	Х							Х							Х	Х	
Serum pregnancy	х																	Only for women of childbearing potential and women with history of tubal ligation

	Screening	Treatment Periods																

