# 9.2. Sample Size Determination

Assuming a 30% screen fail rate, approximately 85 participants will be screened to achieve 60 participants randomly assigned to study intervention for an estimated total of 52 evaluable participants.

The sample of 52 evaluable participants provides about 87% power to the primary endpoint. This calculation is based on a 2-sample t-test, assuming a mean change from baseline to Week 12 in the UAS7 for LY3454738 and for placebo of 17 points and 10 points, respectively, a standard deviation of 7 points for the change from baseline, and a 0.05 two-sided significance level.

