#### 9.4.1. General Considerations

Efficacy analyses will be conducted on the Modified Intent-to-Treat (mITT) Population. This set includes all data from all randomized participants receiving at least 1 dose of the IP according to the treatment the participants were assigned.

Safety analyses will be conducted on the Safety Population. This set includes all data from all randomized participants receiving at least 1 dose of the IP according to the treatment the participants actually received.

All tests of treatment effects will be conducted at a 2-sided alpha level of 0.05, unless otherwise stated. All confidence intervals (CIs) will be given at a 2-sided 95% level. Descriptive summaries of continuous data will present the group mean, standard deviation, median, minimum, maximum, and sample size. Descriptive summaries of discrete data will report the number of participants and incidence as a frequency and as a percentage.

The baseline value for Period 2 is defined as the last nonmissing measurement on or before the date of first study drug administration (expected at Week 0). The baseline value for Period 3 is the last available value before the initial dose in Period 3 (expected at Week 12). Other definitions of the baseline value may be used to conduct additional supporting analyses.

A number of efficacy outcome measures are in the form of weekly scores derived from patient daily diary data. For these measures, the weekly score will be derived from the 7 days immediately prior to the study visit. The baseline score will be derived from the 7 days prior to Day 1.

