# **10.2.** Appendix 2: Clinical Laboratory Tests

Hematology a,b	Clinical Chemistry a,b
Hemoglobin	Sodium
Hematocrit	Chloride
Erythrocyte count (RBCs)	Bicarbonate
Mean cell volume	Potassium
Mean cell hemoglobin	Total bilirubin
Mean cell hemoglobin concentration	Total protein
Leukocytes (WBCs)	Direct bilirubin
Differential	Alkaline phosphatase (ALP)
Neutrophils, segmented	Alanine aminotransferase (ALT)
Lymphocytes	Aspartate aminotransferase (AST)
Monocytes	Gamma-glutamyl transferase (GGT)
Eosinophils	Blood urea nitrogen (BUN)
Basophils	Creatinine
Platelets	Creatine kinase (CK)
Cell morphology	Uric acid
	Calcium
Urinalysis a,b	Glucose
Specific gravity	Albumin
pH	Cholesterol (total)
Protein	Triglycerides
Glucose	
Ketones	Lipid Panel (fasting) a,b,c,k
Bilirubin	High-density lipoprotein
Urobilinogen	Low-density lipoprotein
Blood	
Nitrite	Hormones (female)
Urine leukocyte esterase	Pregnancy test (serum a , b , d , h and urine f)
Microscopic examination of sediment	Follicle-stimulating hormone (FSH) a,b,g
	Stool evaluation a,b,i

table continues

Biomarkers a,b	Serology
C-reactive protein, high-sensitivity I	Tuberculosis (TB) testing:
Receptor occupancy assay I	QuantiFERON-TB Gold test a,b, d or T-SPOT d,j or TST d,j
	HIV testing a , b , d
Serum immunoglobulins (IgG, IgM, IgA, IgE) a	HCV testing:
	Hepatitis C antibody a,b,d,e
Pharmacogenomics sample 	HBV testing:
	Hepatitis B core antibody a , b
Stored Samples 	Hepatitis B surface antigen a , b
Exploratory storage samples:	
Serum	
Plasma	Pharmacokinetic Samples a,1
Whole blood (DNA EDTA)	LY3454738 concentration
RNA	Pharmacokinetics (PK) for immunogenicity (stored)
Immunogenicity Samples a,l	Flow Cytometry a
Anti-LY3454738 antibodies	TBNK panel
Anti-LY3454738 antibodies neutralization	

Abbreviations: DNA = deoxyribonucleic acid; EDTA = ethylenediamine tetraacetic acid; HBV = hepatitis B virus; HCV = hepatitis C virus; HIV = human immunodeficiency virus; RBC = red blood cell; TBNK = T-cells, B-cells, and natural killer (NK) cells; TST = tuberculin skin test; WBC = white blood cell.

- a Assayed by Lilly-designated laboratory.
- b Results will be confirmed by the central laboratory/other at the time of initial testing.
- c For the fasting lipid profile, participants should not eat or drink anything except water for 12 hours prior to test.

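### SAP 5.7.3 compares triglycerides, glucose and total cholesterol from visits with no fasting requirement with a fasted baseline, so any within-arm test against zero there can pick up a meal effect

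*SAP*

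**What the plan says.** **Fasting.** The Schedule of Activities (Protocol 1.3) marks V2, V9 and V16 as fasting visits and no others. The fasting instruction is tied to the lipid profile: "For the fasting lipid profile, participants should not eat or drink anything except water for 12 hours prior to the test". Fasting is waived for the lipid panel at an early termination visit.

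**Sampling.** The same schedule marks clinical chemistry at every visit from V1 to V16 and at the early termination visit.

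**Analyte lists.** Protocol Appendix 2 (10.2) puts glucose, total cholesterol and triglycerides under clinical chemistry. Under the heading that begins "Lipid Panel (fasting" it lists only high- and low-density lipoprotein.

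**Baseline.** SAP 5.3.2 takes the last nonmissing value up to first dosing, expected at Week 0 (V2). For Period 3 the baseline is expected at Week 12 (V9). Both are fasting visits.

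**Analysis.** SAP 5.7.3 covers all analytes specified in the protocol. It says "Change from baseline to each visit will be displayed in box plots for patients who have both a baseline and a result" for the visit in question. It then adds change to last observation, a p-value from an ANCOVA with treatment and baseline, and this sentence: "The significance of within-treatment group LSMean changes from baseline are different from zero using a t-statistic". Neither document has a fasting rule for these analyses.

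**The concern.** Triglycerides and glucose are commonly expected to vary with recent food intake, and the protocol itself asks for a 12-hour fast before the lipid profile. If participants eat before visits where fasting is not required, the change from a fasted V2 includes a meal component. The displays could then show a rise after V2, a drop at V9, another rise and a drop at V16, produced by the visit schedule alone. SAP 5.7.3 intends its box plots of observed values to show trends over time, so the pattern could mislead.

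A between-arm comparison cancels a shift that both arms share. A within-arm test against zero does not: it treats the meal component as change. With unequal arms, the same shift is also more likely to reach p<0.05 in the larger arm. What is at stake is a safety reading of three routine analytes, not the primary endpoint.

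**Working it through.** **1. Allocation.** The plan gives no power figure for laboratory tests. Its primary-endpoint figure serves only to confirm the arm sizes: "The sample of 52 evaluable participants provides about 87% power to the primary endpoint", with means "for LY3454738 and for placebo of 17 points and 10 points" and "a standard deviation of 7 points for the change from baseline". At 3:1, 52 splits into 39 and 13. The standard error is 7 × √(1/39 + 1/13) = 2.24, and 7/2.24 = 3.12. The normal approximation gives Φ(3.12 − 1.96) = 87.7%; the noncentral t gives 86.5%. Both agree with the stated 87%, so 3:1 is the right split: 39:13 of 52 evaluable, or 45:15 of 60 randomized.

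**2. Visits.** V3 to V16 is 14 postbaseline treatment visits, all with chemistry. V9 and V16 are fasting visits. That leaves V3–V8 (6) and V10–V15 (6), so 12 of 14.

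**3. Within-arm test at one such visit.** The documents give neither the size of a fed-versus-fasted shift nor the SD of change, so the shift d, in units of that SD, is an assumption. It is taken as equal in both arms, with no drug effect. The test is two-sided at 0.05 (Protocol 9.4.1; SAP 5.3). For an ANCOVA with pooled error, df = 60 − 3 = 57, the critical value is 2.002, the noncentrality is d√n, and the rejection rate is P(|T| > 2.002).

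| Assumed d | d√45 | n = 45 | d√15 | n = 15 |
|---|---|---|---|---|
| 0 | 0 | 5% | 0 | 5% |
| 0.1 | 0.67 | 10% | 0.39 | 7% |
| 0.2 | 1.34 | 26% | 0.77 | 12% |
| 0.33 | 2.21 | 59% | 1.28 | 24% |
| 0.5 | 3.35 | 91% | 1.94 | 48% |

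With 39:13 (df = 49), d = 0.2 gives 23% and 11%, and d = 0.5 gives 87% (0.865 unrounded) and 42%.

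The formula sets the standard error to SD/√n. A simulation of the full ANCOVA at 39:13, with an assumed baseline-to-visit correlation of 0.5, gave somewhat higher within-arm rates: 57% and 24% at d = 0.3, against 45% and 18% by formula. At d = 0 it gave 7.7% and 6.1%. Adjusting for baseline shrinks the residual SD, while the LSMean's standard error ignores sampling variation in the mean baseline. The table is therefore approximate.

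**4. Test for last observation only.** Completers end at V9 or V16, both fasting visits. Suppose that the 60 − 52 = 8 non-evaluable participants all end on a non-fasting sample, spread evenly over the arms. The mean shift is then d × 8/60. For d = 0.3, 0.5 and 0.8 this is 0.040, 0.067 and 0.107 SD, and the rejection rates are 6%, 7% and 11% with 45 and 5%, 6% and 7% with 15.

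**5. Between-arm ANCOVA.** A common shift cancels in the treatment contrast. The same simulation (10,000 runs per setting) gave rejection rates of 5.1%, 4.7% and 5.2% at d = 0, 0.3 and 0.5.

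**The case against.** The strongest reply is that SAP 5.7.3 may not plan by-visit within-arm tests at all. Change to each visit is to be displayed; change to last observation is to be summarized and analyzed. The p-value and the t-test come after the sentences on last observation. On that reading the rates in step 3 do not arise and only step 4 applies. This stands as a fair reading, but the text does not settle it, and the by-visit change plots mix fasting states either way.

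Three further limits stand in full.

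- The schedule does not require fasting at the 12 visits; it does not say that participants have eaten. The true shift may be near zero, and at 0.1 SD the inflation is modest.
- Both arms appear in the same display beside an unbiased between-arm p-value, so a shared shift should be visible.
- No decision rule depends on a within-arm p-value. These analytes are neither adverse events of special interest (Protocol 8.3.7) nor special safety topics (SAP 5.7.6).

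A reader might infer that all 12 visits threaten a false metabolic signal on LY3454738 because its arm is three times larger. The documents do not support that. The larger group is on drug only in Period 2, so only V3–V8 qualify. At V10–V15 it receives placebo, and under the treatment-received rule in SAP 5.3.1 the asymmetry reverses. SAP 5.7 instead keeps the Week 0 label; the two sections need reconciling separately.

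**Conclusion.** The mismatch is real and minor. For triglycerides, glucose and total cholesterol, SAP 5.7.3 compares samples with no fasting requirement with a fasted baseline at 12 of 14 postbaseline treatment visits, and for some early terminators' last observation. A within-arm test there cannot separate a meal effect from a drug effect.

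The size depends on two things that the documents leave open: whether the within-arm test is run by visit, and how large any meal shift is. By visit, the false-positive rate lies between near nominal and very high over a plausible span of assumptions. For last observation only, it stays at about 6–11% in the larger arm under the step 4 assumptions. The drug-versus-placebo comparison is unaffected if the shift is common to both arms, and the primary analysis is not involved. The documents do not establish that a false rise will occur, or that it would fall on the drug arm throughout.

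**What to change.** Add a short rule to SAP 5.7.3 for triglycerides, glucose and total cholesterol:

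- Run within-arm tests against zero only between fasting visits: V2 to V9 for Period 2, and V9 to V16 for Period 3.
- Define last observation as the last value from a fasting visit.
- At the other visits keep the box plots and the between-arm comparison, label them as visits where fasting was not required, and omit within-arm p-values.

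For all analytes, state whether the within-arm test applies at each visit or only to last observation.

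The rule removes the mismatch if participants fast as scheduled, and it needs no new samples. The cost is the loss of within-arm tests at non-fasting visits. Early terminators with no postbaseline fasting value also drop out of the last-observation analysis for these three analytes. Dropping all change analyses at the 12 visits would cost more, because it would also discard the between-arm comparison, which a common shift does not bias.
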